**Table 1: PLWH who initiated ART 2013-2015 (N=762)**

HTN prevalence	12%
Pre-HTN prevalence	22%
Proportion of pre-HTN PLWH who developed HTN in 18 months	38%

**Figure 3:**

**Prevalence of Elevated 10-year CVD risk among HIV-infected and uninfected adults**

The definition of pre-HTN and HTN according to WHO, international and Haitian Ministry of Health guidelines are listed in Table 2. The relationship between SBP >115 mm Hg and CVD

events is linear, with multiple epidemiological studies reporting increased risk of CVD, renal disease, and all-cause mortality among adults with pre-HTN. Untreated pre-HTN is a progressive condition of ongoing arteriolar hypertrophy, endothelial dysfunction, and stimulation of the renin-angiotensin system which lead to further HTN. Landmark trials and meta-analyses have shown that 1) treatment of pre-HTN in patients with diabetes, chronic kidney disease, and nonobstructive coronary disease decreases CVD events and disease progression, and 2) use of antihypertensive treatment among individuals with pre-HTN can prevent progression to HTN. These data led to revised guidelines recommending antihypertensive treatment at lower BP thresholds among individuals with these diseases. In 2017, the US guidelines went further to recommend antihypertensive treatment for high-risk adults with SBP  $\geq$ 130 or DBP  $\geq$ 80 mm Hg, but HIV is not currently included as a high-risk category.

HIV is associated with equal, if not greater, CVD risk as diabetes; yet, the WHO still recommends PLWH initiate antihypertensive treatment at the same BP threshold as adults without HIV. Data are needed to clarify if initiation of antihypertensive treatment among PLWH with pre-HTN can prevent progression to HTN, and ultimately CVD-related mortality. The proposed pilot trial is the first step to explore the feasibility, benefits, and risks of initiating antihypertensive treatment among PLWH with pre-HTN in a well-established HIV program in Haiti, one of the poorest countries in the world. Knowledge gaps include: Is it feasible to initiate and integrate antihypertensive treatment into HIV care among relatively healthy PLWH with pre-HTN? Could initiating antihypertensive treatment worsen HIV outcomes? What is the BP reduction using amlodipine (which is Haiti's first-line antihypertensive medication) among PLWH with pre-HTN? Data from this pilot trial will inform the design of a future multicenter trial powered for incident CVD events. **Our goal is to change guidelines** to lower the BP threshold for initiation of antihypertensive medications among PLWH, should earlier HTN treatment prevent CVD.

Table 2: Summary of WHO and Haitian HTN definitions and guidelines		
Category	Definition	Threshold for initiation of antihypertension treatment
Normal	SBP < 120 and DBP < 80	
Pre-HTN	SBP 120-139 or DBP 80-89	Diabetes & Chronic Kidney Disease (at SBP $\geq$ 130 or DBP $\geq$ 90)
HTN	SBP $>$ 140 or DBP $>$ 90	General adults including PLWH

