## Protocol Summary

**Title:** Prehypertension in Haiti

**Study Summary:** We propose an unblinded pilot RCT of 250 persons living with HIV (PLWH), aged 18-65 years, who receive ART care at GHESKIO, are virally suppressed, and have pre-HTN (SBP 120-139 or DBP 80-89 mm Hg) to be randomized to **early HTN treatment** versus **standard of care** (SOC). Participants will be recruited from GHESKIO's HIV clinic. Eligible individuals will complete informed consent and be randomized to early HTN treatment vs. SOC. Participants in early HTN treatment will initiate amlodipine immediately versus those in SOC will initiate amlodipine only if they meet the HTN threshold during the study period. All participants will be followed for 12 months. The primary outcome is mean change in SBP at 12 months between study arms. Secondary outcomes are viral suppression, medication adherence, adverse events, and acceptability. We will also assess CVD risk factors and myocardial/vascular dysfunction among all participants at enrollment.

**Population:** We will recruit 250 PLWH from GHESKIO'S HIV Clinic. Inclusion criteria: PLWH 18-65 years of age, ART duration  $\geq$  1 year , stable regimen  $\geq$  6 months, HIV 1-RNA  $<$  1,000 copies/mL within past 12 months, Pre-HTN (SBP 120-139 or DBP 80-89 mm Hg), no current antihypertensive treatment, receives HIV care at GHESKIO, and willing to provide consent. Exclusion criteria: pregnancy, kidney disease, diabetes, advanced illness with limited life expectancy, plans to move out of the area within the next year, and clinician determination that patient is unstable on ART.

**Number of Sites:** Single site: GHESKIO Center Port au Prince, Haiti

**Study Duration:** 2 years

**Subject Duration:** 12 months

**Primary Aim:** To assess the feasibility of initiating antihypertensive treatment among PLWH with pre-HTN through a pilot randomized controlled trial comparing early HTN treatment to SOC. Feasibility outcomes include enrollment and retention data, proportion who initiate amlodipine, and incremental change in SBP at 12 months between arms. The pilot trial has  $\geq$ 80% power to detect differences in change in SBP  $\geq$  4 mm Hg.

**Secondary Aims:** To also examine the following outcomes and measures:

- a. Viral suppression compared between study arms at 12 months (defined as HIV-1 RNA  $<$  1000 copies/ml)

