### 4.3 Study Population

The study population will include 250 PLWH from GHESKIO’s HIV clinic. Inclusion and exclusion criteria are in Table 3. We included younger PLWH given the early onset of HTN in Haiti and limited the upper age to 65 years given the low incidence of HIV above this age. We exclude PLWH with kidney disease ( $<60$ mL/min/1.73m $^2$  using CKD-Epi equation) because Haiti’s guidelines recommend furosemide as first-line treatment for this group. We exclude diabetics (defined as fasting glucose  $\geq 126$  mg/dL or non-fasting glucose  $\geq 200$  mg/dL, or taking diabetes medications) because Haiti’s guidelines recommend initiation of antihypertensive medications when SBP  $\geq 130$  mmHg or DBP  $\geq 80$  mmHg. Individuals on a protease inhibitor with ritonavir will be excluded as ritonavir can increase levels of amlodipine. Women who become pregnant will be censored at time of pregnancy.

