**Table 3. Inclusion and exclusion criteria for the trial**

Inclusion criteria	Exclusion criteria

 
• PLWH 18-65 year of age
 
• ART duration <math>\geq 1</math> year, stable regimen <math>\geq 6</math> months
 
• HIV 1-RNA <math>< 1,000</math> copies/mL within past 12 months
 
• Pre-HTN (SBP 120-139 or DBP 80-89 mm Hg)
 
• No current antihypertensive treatment
 
• Receives HIV care at GHESKIO
 
• Willing to provide consent
 
	
 
• Pregnancy
 
• Kidney disease or diabetes
 
• Protease inhibitor/ritonavir
 
• Advanced illness with limited life expectancy
 
• Plans to move out of the area within the next year
 
• Clinician determination that patient is unstable on ART
 

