#### **4.4 Recruitment and Informed Consent**

Screening and recruitment will follow GHESKIO Clinical Trials Unit procedures that have been highly successful in NIH trials. We will identify and invite potential participants both 1) in-person at GHESKIO's HIV clinics using real time BP measurements and 2) from GHESKIO's electronic medical record (EMR) using BP measurements in the past 12 months, age, ART duration, viral suppression, and no current antihypertensive treatment. PLWH meeting these eligibility criteria will be tagged in the EMR as participants for recruitment and a list will be given to the study team.

The research nurse will approach patients in the HIV clinics, or call PLWH on the list to introduce the study and invite interested individuals for informed consent and then a screening visit. After confirming basic eligibility criteria, the research nurse will initiate informed consent procedures among eligible participants. The informed consent process consists of two education sessions, followed by assessment of understanding and written informed consent.

After informed consent, participants will be assigned a unique study ID number and undergo a screening visit with review of eligibility criteria and screening labs. Pre-HTN is defined as  $\geq 2$  BP measurements of SBP 120-139 mm Hg or DBP 80-89 mm Hg on separate days. All BP measurements will be done according to AHA/WHO guidelines. Screening labs will be collected (urine or serum pregnancy test, fasting or random glucose, and creatinine) to evaluate if the patient is pregnant, has diabetes, or kidney disease. We will document the number screened and reasons for study exclusion.

In 2018, 18,872 PLWH on ART received care at GHESKIO with mean duration of ART of 5.6 years, 76% on first-line regimens, 86% virally suppressed, and median age of 35 years. We estimate 3,819 PLWH at GHESKIO satisfy the eligibility criteria. Based on our past enrollment experience, we are confident 250 participants can be enrolled from this sampling frame in 6 months.

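### Known, untreated coronary disease is not an exclusion, although the rationale counts nonobstructive coronary disease among the conditions helped by treating pre-HTN

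*Combined protocol and SAP*

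**What the plan says.** Section 2.2 (Scientific Rationale, the paragraph after Figure 3) says that landmark trials and meta-analyses show that "treatment of pre-HTN in patients with diabetes, chronic kidney disease, and nonobstructive coronary disease decreases CVD events and disease progression". It continues: "These data led to revised guidelines recommending antihypertensive treatment at lower BP thresholds among individuals with these diseases". Three diseases are named.

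The eligibility rules cover two of them. The Protocol Summary reads "Exclusion criteria: pregnancy, kidney disease, diabetes, advanced illness with limited life expectancy, plans to move out of the area within the next year", followed by instability on ART. The disease entry in Table 3 is "Kidney disease or diabetes". Section 4.3 explains both choices by Haitian guidance. Diabetics are left out because Haiti's "guidelines recommend initiation of antihypertensive medications when SBP" is at least 130 mm Hg or DBP at least 80. Kidney disease is left out because its first-line drug is furosemide. In the pre-HTN row of Table 2, the entry for starting treatment is "Diabetes & Chronic Kidney Disease".

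Section 4.4 finds candidates in clinic by BP reading, or in the EMR "using BP measurements in the past 12 months, age, ART duration, viral suppression, and no current antihypertensive treatment". Screening labs are drawn "to evaluate if the patient is pregnant, has diabetes, or kidney disease". Section 4.5 and Table 4 place CVD history, ECG, echocardiography and vascular ultrasound at the enrollment visit, where randomization also occurs. Under sections 4.6 and 4.7, SOC participants start amlodipine only once they reach 140 systolic or 90 diastolic.

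**The concern.** The protocol tells its reader that treating pre-HTN in nonobstructive coronary disease reduces events. It then leaves people with that disease eligible for an arm that defers treatment. One of the references behind the statement is a trial in coronary disease with normal blood pressure. Section 3.1 describes that trial as testing amlodipine 10 mg daily in normotensive adults with existing cardiovascular disease, which is the study drug at its top dose.

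What is at stake is the protection of a few individuals. Someone whose coronary disease is already on record, and who takes no antihypertensive, could be randomized to wait up to 12 months for a drug that the protocol's background says would help. Nothing here bears on the validity of the SBP comparison.

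**Working it through.** **1. Could such a person enter?** Each step before randomization was checked for anything that would stop them.

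| Step | What it checks | Catches known, untreated coronary disease? |
|---|---|---|
| Protocol Summary, Table 3 | Pregnancy, kidney disease, diabetes, ritonavir-boosted PI (Table 3), life-limiting illness, relocation, ART instability | No |
| Inclusion: not on antihypertensives | Current drugs | Only those already treated |
| EMR search (4.4) | BP, age, ART duration, viral suppression, treatment | No |
| Screening labs (4.4) | Pregnancy, glucose, creatinine | No |
| Enrollment visit (4.5, Table 4) | CVD history, ECG, imaging | Recorded, but no result bars randomization |

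The exclusion for life-limiting illness would not ordinarily reach nonobstructive disease. The gap is therefore real, but confined to disease that is both known and untreated.

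**2. How many?** The documents give no prevalence of known, untreated coronary disease. The figures 250 and 3,819 and the clinic's median age of 35 years come from section 4.4. The prevalence p is an assumption, taken from 0.1% to 2%.

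- SOC arm: 250 / 2 = 125.
- Prevalence at which one SOC case is expected: 1 / 125 = 0.80%.
- Prevalence giving an even chance of at least one SOC case: 1 − 0.5^(1/125) = 0.55%.
- Expected SOC cases, 125p: 125 × 0.001 = 0.125, up to 125 × 0.02 = 2.5.

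**3. What would an exclusion cost in recruitment?** The same p is applied to the estimated eligible pool.

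- Now: 3,819 / 250 = 15.28 eligible people per place.
- Removed, 3,819p: 3.8 to 76.4 people.
- Left per place, 3,819(1 − p) / 250: 15.26 to 14.97.

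The plan states no figure on this point to reproduce. The stated 80% power plays no part in the argument.

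**The case against.** The strongest reply is that the exclusions are consistent with the guidance they rest on. Section 4.3 ties both to Haitian recommendations, not to the trial evidence in section 2.2. The kidney exclusion concerns the choice of drug, not a threshold, so the match of two diseases out of three is partly coincidence. Table 2 lists no lower threshold for coronary disease. A reader might infer that the SOC arm withholds treatment due under local care, or that the reason for excluding diabetics carries over directly to coronary patients. The documents support neither reading: they contain no Haitian recommendation to treat coronary disease in the pre-HTN range.

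Safeguards also exist. Table 4 schedules BP checks for SOC participants at months 1, 2, 3, 5, 6, 8, 9 and 12, against six-monthly clinic visits for virally suppressed patients in routine care. Everyone has an ECG and imaging at enrollment. Disease found through study procedures is referred, free of charge, to clinicians outside the research team, and nothing bars those clinicians from treating.

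All of this stands and keeps the severity low. It does not remove the mismatch. The protocol reports benefit in this disease, leaves people known to have it eligible, and asks about it too late to affect assignment. The referral provision is written for disease diagnosed through study procedures, so it does not clearly cover disease that was already known. An exclusion would also take a few people out of the baseline description in secondary aims e and f. That is a fair cost to count.

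**Conclusion.** The point holds as a low-severity, inexpensive improvement. Followed as written, the plan could assign a person with known, untreated coronary disease to defer amlodipine to 140/90 mm Hg, against the protocol's own account of the evidence. It shows no departure from Haitian standard of care and no misapplication of Table 2, and it gives no reason to doubt the primary endpoint or the power.

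The size is uncertain and probably very small. Under the assumed prevalence of 0.1% to 2%, the expected number in the SOC arm is 0.1 to 2.5. The median age of 35 and the requirement to be off antihypertensives both suggest few such people. The conclusion relies on section 2.2's summary of the trials and guidelines as the protocol gives it, since the sources themselves were not available.

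**What to change.** 1. Add known coronary disease, by history or EMR diagnosis, to the exclusions in the Protocol Summary and Table 3, and add the same term to the EMR filter in section 4.4. The wording is deliberately wider than nonobstructive disease, because a history or diagnosis code may not separate the two.
2. In Table 4, move the existing CVD-history item from ENROLL to SCREEN, so that it is answered before randomization. Section 4.4 already provides a screening visit after consent, so no new visit or test is needed.

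The cost is one exclusion line in two places, one filter term and one item moved. Under the assumed range, about 4 to 76 of the 3,819 estimated eligible people would be lost. Generalizability narrows slightly, and a few people with known disease drop out of descriptive aims e and f. The sample size, endpoints and analysis are unchanged.

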### 3 POTENTIAL RISKS AND BENEFITS

#### 3.1 Potential Risks

The risks of this study include loss of confidentiality of study participation, social harms, discomfort, and phlebotomy, and adverse events of medications. GHESKIO has experience conducting research studies and has produced teaching materials in Creole for the risks involved in these studies during the informed consent process. Further, the occurrence of these adverse events will be closely monitored by the study team and reported to the DSMB and IRB.

- A. Loss of Confidentiality: There is a potential loss of confidentiality of information provided during the study including one's HIV status or diagnosis of hypertension through participation in the study.
- B. Social Harms: Participants may experience social harms including loss of privacy, or social stigma from perception of being involved in a study related to HIV and cardiovascular disease risk factors, such as hypertension. HIV-infected adults are a particularly stigmatized population at heightened risk of social harms.
- C. Discomfort: Participants will be asked to complete a questionnaire at study enrollment and at the 12 months study visit. The questionnaire includes topics that may be sensitive such as family history and health behaviors including smoking, alcohol, physical activity, and diet.
- D. Phlebotomy: There is a slight risk of physical discomfort (i.e., slight bruising or tenderness at the phlebotomy site) to participants associated with collection of blood sample for hematology, chemistry, and HIV viral load. Approximately 15 mL of venous blood will be collected by phlebotomy at study enrollment for these laboratory measures. Approximately 5 mL of venous blood will be collected by phlebotomy for HIV viral load testing at the 12-month study visit.
- E. Adverse events: Amlodipine is recommended by the WHO as first-line medication for elevated blood pressure and has a safe side effect profile. The most common side effects of amlodipine are dizziness and or lightheadedness and peripheral edema. We will monitor adverse events using DAIDS criteria for hypotension, peripheral edema and other side effects reported by participants that are related to amlodipine. In other studies, a dose of amlodipine 10mg daily is associated with ~ 5-6 mm Hg reduction in SBP over 1 month. In one clinical trial (CAMELOT), which evaluates the use of amlodipine 10 mg daily among normotensive adults with existing cardiovascular disease, 3.3% of participants reported symptoms of lightheadedness and dizziness for which amlodipine was discontinued and 5% discontinued amlodipine due to peripheral edema. We anticipate a similar rate of side effects and adverse events in this study.

#### Protection against risks:

The following measures will minimize study risks:

- A. Loss of Confidentiality: Each participant will be assigned a study identification number consisting of a unique code unrelated to any patient identifying information, as per Good Clinical Practice guidelines. Any identifiers linked to the participant will be secured and only available to staff at

the GHESKIO Research Center, to ensure subject confidentiality. Only authorized professionals collaborating with the principal investigator will have access to the information. All samples and subject data will be coded at the GHESKIO Research Center with the study identification number. All source documents will be kept in locked file cabinet. GHESKIO computers and servers are protected by firewall protection and are only accessible with a password. Study staff will be trained in Good Clinical Practice regarding maintaining confidentiality. Participants will be asked to report any breeches in confidentiality, and these will be reported to the DSMB.

- B. **Social Harms:** Research staff are trained on how to respond to any social harm reported by a participant. Staff performance will be monitored by the study director, [name] during quality assurance assessments to ensure minimization of social harms. Doctors [name], [name], and [name] will be available to assist the study staff in responding to any event that requires further management. We routinely educate all patients in the GHESKIO clinic on the importance of confidentiality and not sharing information with other patients. Participants will be encouraged to report any adverse event or social harms including loss of confidentiality and stigma to study staff. These will be documented in source documents and reported to the study team on standardized adverse event forms.
- C. **Discomfort:** As part of the informed consent process, all potential participants will be instructed that they do not have to disclose personal information that they are uncomfortable sharing and that they can withdraw from the study at any time.
- D. **Phlebotomy:** Participants will be informed of the possible risks of slight bruising or tenderness at the site of the blood draw. They will be encouraged to call or visit the study site if symptoms persist or worsen.
- E. **Adverse events:** Participants will be informed of the possible side effects of amlodipine including hypotension and peripheral edema. We will grade the signs and symptoms of hypotension and peripheral edema, or any other reported side effect, using existing DAIDS criteria(11) and report Grade III-V events to the DSMB and the GHESKIO and Weill Cornell IRB. Study staff will screen for drug-related adverse events at every study visit. Participants who report adverse events will discuss them with their clinical (non-research) physicians and decide together if amlodipine should be discontinued. All clinical care of any adverse event will be provided free of charge by GHESKIO.

### 3.2 Known Potential Benefits

The proposed study has the potential to change the paradigm of antihypertensive treatment in PLWH, both in the US and abroad. If the study finds earlier initiation of antihypertensive treatment is a form of CVD prevention, then we can reduce CVD events and related mortality in PLWH.

Participants in the proposed study will also benefit from having free screening for hypertension and free medications. Moreover, participants who are diagnosed with a cardiovascular risk factor, abnormal laboratory value (e.g. elevated hemoglobin A1C), and/or other diseases will be referred to ongoing clinical care at GHESKIO or a GHESKIO-affiliated hospital. GHESKIO is affiliated with 4 hospitals in Port-au-Prince including Hospital Bernard Mevs, Hospital du Canape, Hospital Saint-Damien, and Hospital Saint Francois de Sales. **Receipt of clinical care is not dependent on study**

**participation.** The GHESKIO NCD Research Unit follows national guidelines for the management of chronic diseases including hypertension, diabetes, kidney disease, among others. All WHO Essential Medications are available at the clinic including aspirin, amlodipine, hydrochlorothiazide, hydralazine, bisoprolol, enalapril, digoxin, metformin, insulin, among others. The GHESKIO affiliated hospitals provide free care to patients who cannot pay.

If the intervention study arm, early HTN treatment, is found to be effective in the primary study outcome of reduced mean SBP  $\geq 4$  mm Hg between study arms, we will continue amlodipine in participants randomized to the intervention arm and offer amlodipine to all participants in the standard of care study arm.

